### 8.5.2.1 Secondary Clinical Endpoint(s)

- The frequency of the maximum observed grade of each toxicity. Incidence and severity of adverse events and laboratory abnormalities, graded according to CTCAE v4.0 [2].
- To evaluate the PSA50 response
  - PSA50 response is defined as at least a 50% decline in PSA from baseline value
- Median time to radiographic progression using (RECIST and PCWG2 criteria for soft tissue and bone lesions, respectively, as assessed by the investigator).

#### Exploratory Objectives:

- Median time to PSA progression based on Prostate Cancer Working Group 2 (PCWG2) criteria [1]:
  - in patients with no PSA decline from baseline as:  $\geq 25\%$  increase from the baseline value and an increase in absolute value of  $\geq 2$  ng/mL, at least 12 weeks from baseline
  - in patients with an initial PSA decline from baseline as:  $\geq 25\%$  increase and an absolute increase of  $\geq 2$  ng/mL above the nadir value, which is confirmed by a second value obtained three or more weeks later
- Median time to ALP progression.
  - in patients with no ALP decline from baseline as:  $\geq 25\%$  increase from the baseline value, at least 12 weeks from baseline
  - in patients with an initial ALP decline from baseline as:  $\geq 25\%$  increase above the nadir value, which is confirmed by a second value obtained three or more weeks later.
- Median time to pain progression defined as use of opioid analgesics for cancer-related pain.
- Median time to occurrence of first skeletal related event (SRE):
  - the use of external beam radiotherapy to relieve skeletal symptoms or the occurrence of new symptomatic pathological bone fractures (vertebral or non-vertebral) or the occurrence of spinal cord compression or a tumor related orthopedic surgical intervention.
- Median time to occurrence of first start of chemotherapy use.

## 8.6 Analyses

Version 4.0 Date: 08/21/2020

NCT02463799

The values for radium-223 in this protocol has been revised as per the US NIST standardization update (agreed on 17 Mar 2015)

### 8.6.1 Subject Disposition

Subject disposition will include, but will not be limited to, the following:

- Number of subjects registered.
- Number of subjects infused.
- Number of subjects who prematurely discontinued the study (i.e., refused further study assessments [with the possible exception of survival status]).
- Reason(s) for premature discontinuation from the study.
- Number of subjects who died.
- Cause of death summary.
- Number of subjects in the immune response and safety analysis sets.

In addition, the number of subjects screened for the trial will be summarized for the overall study population.

### 8.6.2 Demographics and Baseline Characteristics

Demographic information and baseline disease information and characteristics will be summarized with descriptive statistics for all analysis populations.

### 8.6.3 Efficacy Analyses

The primary efficacy analysis will compare the two randomized groups in terms of SI measured 6 weeks after the first infusion of sipuleucel-T. We will compute the logarithms of each patient's SI and use these data in a t test to compare the two groups.

A secondary analysis will look at the trends in SI over time. This analysis will consist of a repeated measurement analysis of immune response over time evaluated using PA2024-stimulated T cell proliferation via H-thymidine uptake based on the immune response population. The logarithm of response will be used for analysis. Fixed-effect terms in the model will include treatment arm, visit as a class effect, and a treatment-by-visit interaction. The correlation of responses across time within a subject will be modeled using several candidate variance-covariance structures including unstructured, compound symmetry, heterogeneous compound symmetry, autoregressive, and heterogeneous autoregressive. The variance-covariance structure providing the smallest Bayesian information criteria will be selected for the final model. Fixed-effect terms in the model will be tested for significance using type III sums of squares. The formal test for difference between the studies will be based on the p-value for the treatment effect unless we find a significant treatment-by-visit interaction ( $p < 0.05$ ), in which case by-visit treatment comparisons will be made using appropriate contrast statements.

Version 4.0 Date: 08/21/2020

NCT02463799

The values for radium-223 in this protocol has been revised as per the US NIST standardization update (agreed on 17 Mar 2015)

Estimates of treatment effect and corresponding 95% CIs will be provided on the ratio scale obtained by exponentiation of the model derived treatment effect and CI on the logarithm scale.

Immune responses over time for other assays will be analyzed using identical methods described for the primary efficacy analysis, except for the IFN $\gamma$  ELISPOT which we will analyze using ranks instead of on the logarithm scale.

Because PSA and imaging scans are conducted at different time points across the two groups, the time-to-event secondary clinical endpoints will be summarized using generalized Kaplan-Meier methods for interval censored data and displayed graphically where appropriate

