## 1.2 Study Agents

### 1.2.1 Sipuleucel-T

Sipuleucel-T is an autologous cellular immunotherapy product designed to stimulate an immune response against prostate cancer. It consists of autologous peripheral blood mononuclear cells (PBMCs), including antigen presenting cells (APCs, defined as large CD54-positive PBMCs) that have been activated in vitro with prostate antigen PA2024, a recombinant fusion protein composed of prostatic acid phosphatase (PAP) linked to granulocyte-macrophage colony-stimulating factor (GM-CSF).

Sipuleucel-T was approved in the United States in 2013 for the treatment of men with asymptomatic or minimally symptomatic mCRPC. In the pivotal trial D9902B (IMPACT), 512 patients were randomized 2:1 to receive sipuleucel-T (N=341) or control (N=171) [7]. Overall survival was longer in the sipuleucel-T group (median of 25.8 months versus 21.7 months; hazard ratio (HR) =0.78; 95% confidence interval (CI): 0.62, 0.98; P=0.03). More than 3,339 infusions of sipuleucel-T and control (a product manufactured from PBMCs without activation with the PA2024 antigen), have been administered to men with prostate cancer in clinical trials.

Clinical data to support the safety of sipuleucel-T are provided from 904 subjects (sipuleucel-T, N=601; control, N=303) who participated in 4 multicenter, randomized, double-blind, controlled Phase 3 studies. Three of these studies were conducted in men with mCRPC (studies D9902B, D9901, and D9902A), and 1 study was conducted in men with androgen dependent prostate cancer (ADPC) [5-7;16]. In the 4 randomized Phase 3 studies, AEs reported in  $\geq 20\%$  of all subjects were chills, fatigue, pyrexia, and back pain. The most common AEs (observed in  $\geq 5\%$  of sipuleucel-T subjects as well as at least twice the rate of that in control subjects) included chills, pyrexia, headache, myalgia, influenza-like illness, and hyperhidrosis. The majority of these events occurred within 1 day of infusion; were grade 1 or 2 in severity; and were generally of short duration (i.e., resolved in  $\leq 2$  days). Grade 3 or 4 events were reported in 27.6% of subjects in the sipuleucel-T group, compared with 28.4% in the control group.

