## **3.0 STUDY DESIGN**

This is a randomized study designed to assess the antigen-specific immune response of sipuleucel-T with or without radium-223.

Eligible subjects will be registered and randomly assigned in a 1:1 ratio to receive sipuleucel-T and radium-223 or sipuleucel-T alone;

Version 4.0 Date: 08/21/2020

NCT02463799

The values for radium-223 in this protocol has been revised as per the US NIST standardization update (agreed on 17 Mar 2015)

Arm 1: 6 infusions of radium-223 with 3 infusions of sipuleucel-T starting after second dose of radium-223

Arm 2: 3 infusions of sipuleucel-T alone

Subjects in both arms will undergo a standard 1.5 to 2.0 blood volume leukapheresis, followed approximately 3 days later by an IV infusion of sipuleucel-T. This process will occur a total of 3 times at approximately 2-week intervals. Subjects in Arm 1 will receive a total of 6 infusions of radium-223 at IV dose of 50 kBq/kg (55 kBq/kg after implementation of the NIST update) at 4-week interval.

All participants are allowed to receive the best supportive care which includes secondary hormonal manipulation (including flutamide, bicalutamide or nilutamide-but not abiraterone or enzalutamide) as required. No chemotherapy, external-beam radiation, or other radionuclides are allowed while on active treatment but are permitted after completion of active treatment. Glucocorticoid-containing treatments should be minimized to less than the equivalent dose of prednisone 10mg daily if feasible for the 3 months following sipuleucel-T therapy. All patients continue medical or surgical castration during treatment.

[figure not shown]
**Research visits** will be scheduled at screening, at each radium-223 infusion, prior to each leukapheresis (preleukapheresis visit), and week 32, 45 and 58 for Arm 1 (radium-223 and sipuleucel-T combination arm) and at screening, prior to each leukapheresis (preleukapheresis visit), and week 6, 10, 14, 26, 39, and 52 for Arm 2 (sipuleucel-T alone arm) for physical examinations, vital signs, ECOG performance status, adverse event (AE) monitoring, anticancer therapies, first opioid use for cancer-related pain, and laboratory tests. Serum PSA will be assessed at baseline, and week 16, 32, 45, and 58 for Arm 1 and at baseline, and week 10, 26, 39, and 52 for Arm 2. There is a  $\pm 7$  day window for each visit to accommodate holidays, vacations, etc.

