**Imaging studies** including bone scintigraphy test (bone scan) or Na-F PET or C11 acetate PET and abdomen/pelvis CT or MRI will be obtained at screening and week 16, 32, 45, and 58 for Arm 1 and at screening and week 10, 26, 39, and 52 for Arm 2. After the last study visit, imaging studies will be obtained according to the participating institution's standard and/or at the investigator's discretion.

**Immune monitoring** blood samples will be drawn at screening and at 6, 10, 14, 26, 39, and 52 weeks after the first infusion of sipuleucel-T in both arms. Additional blood samples will be obtained at baseline, first pre-leukapheresis visit (only in Arm 1), and weeks 14 and 52 post the first infusion of sipuleucel-T for exploratory antigen spread assessment.

After last study research visit at week 58, safety, treatment-related AEs, survival status, PSA, first opioid use for cancer-related pain (if applicable), and anticancer therapies will be assessed every 3 months for additional 1 year or until the subject's death.

The study design is illustrated in Figure 1.

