Abbreviations: AE = adverse event; A/P = abdomen/pelvis; CT = computed tomography; ECOG = Eastern Cooperative Oncology Group; F/U = follow up visit; Im = Immune assessment visit; JH = Johns Hopkins; MRI = magnetic resonance imaging; PAP = prostatic acid phosphatase; P/E = physical exam; PET = positron emission tomography; Sip = sipuleucel-T infusion visit; PS = performance status; PreL = preleukapheresis visit; PSA = prostatic specific antigen; Rad = radium-223 infusion visit; SAE = serious adverse event; Tx = treatment

- a. All screening procedures must occur within 28 calendar days prior to registration, with the exception of written informed consent, histological documentation of prostate cancer with Gleason grading, and imaging for confirmation of metastatic disease
- b. Radium-223 visits will occur 6 times at weeks 0, 4, 8, 12, 16, and 20
- c. Applies to all leukapheresis; pre-leukapheresis visits will occur  $\leq 5$  days prior to each leukapheresis. First sipuleucel-T infusion may occur any time between the second and third radium-223 infusion.
- d. At baseline, week 6, 10, 14, 26, 39, and 52 post-first sipuleucel-T infusion
- e. Follow-up visits will occur at every 3 months after week 58 visit for additional 1 year or until the subject's death
- f. Vital signs will be measured 1 to 30 minutes prior to, and at 30 minutes ( $\pm 10$  min) following each infusion
- g. Bone scan and CT or MRI abdomen/pelvis
- h. Per institution's standard procedure/at the investigator's discretion
- i. Only treatment-related events will be collected
- j. Baseline sample can be drawn at subject's "day one visit" (prior to dosing). See Appendix 1 for sample preparation instructions.
- k. Blood samples for antigen spread analysis will be collected at baseline (can be drawn at subject's "day one visit" (prior to dosing) , 1st pre-leukapheresis visit, and weeks 14 and 52 post-first sipuleucel-T infusion.
- l. PTT, PT/INR

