## b. Arm 2: sipuleucel-T alone

	Screen a Im-1	PreL-1 b	Sip-1	PreL-2 b	Sip-2	PreL-3 b	Sip-3	Im-2 c	Im-3 c	Im-4 c	Im-5 c	Im-6 c	Im-7 c	F/U d
Week	Week	0	0	2	2	4	4	6 c	10 c	14 c	26 c	39 c	52 c	
Week														
Informed consent	X													
Registration/	X													
Pathology	X													
Sip-T infusion			X		X		X							
Clinical Assessments														
Medical History	X													
P/E	X	X		X		X								
Vital Signs	X	X	X e	X	X e	X	X e	X	X	X	X	X	X	
ECOG PS	X	X		X		X		X	X	X	X	X	X	
Imagingf	X									X	X	X	X	X g
Safety Assessment														
AEs/SAEs		X	X	X	X	X	X	X	X	X	X	X	X	X h
Medication														
Anticancer Tx	X	X		X		X								X
1 st Opioid use	X	X		X		X								X
Survival Status														
Lab Assessments														
Hematology	X	X		X		X								
Chemistry/ LDH/ magnesium / phosphorus	X	X		X		X								
Testosterone	X													
PSA	X								X		X	X	X	
Coagulation k	X													
Immune Assessments														
Dendreon l	X							X	X	X	X	X	X	
JH Lab j	X									X			X	

Version 4.0 Date: 08/21/2020

NCT02463799

The values for radium-223 in this protocol has been revised as per the US NIST standardization update (agreed on 17 Mar 2015)

Abbreviations: AE = adverse event; A/P = abdomen/pelvis; CT = computed tomography; ECOG = Eastern Cooperative Oncology Group; F/U = follow up visit; Im = Immune assessment visit; JH = Johns Hopkins; MRI = magnetic resonance imaging; PAP = prostatic acid phosphatase; P/E = physical exam; PET = positron emission tomography; Sip = sipuleucel-T infusion visit; PS = performance status; PreL = preleukapheresis visit; PSA = prostatic specific antigen; SAE = serious adverse event; Tx = treatment

- a. All screening procedures must occur within 28 calendar days prior to registration, with the exception of written informed consent, histological documentation of prostate cancer with Gleason grading, and imaging for confirmation of metastatic disease
- b. Applies to all leukapheresis; pre-leukapheresis visits will occur  $\leq 5$  days prior to each leukapheresis
- c. At baseline, week 6, 10, 14, 26, 39, and 52 post-first sipuleucel-T infusion

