- d. Follow-up visits will occur at every 3 months after week 58 visit for additional 1 year or until the subject's death
- e. Vital signs will be measured 1 to 30 minutes prior to, and at 30 minutes ( $\pm 10$  min) following each infusion
- f. Bone scan and CT or MRI abdomen/pelvis
- g. Per institution's standard procedure/at the investigator's discretion
- h. Only treatment-related events will be collected
- i. Baseline sample can be drawn at subject's "day one visit" (prior to dosing). See Appendix 1 for sample preparation instructions.
- j. Blood samples for antigen spread analysis will be collected at baseline (can be drawn at subject's "day one visit" (prior to dosing), and weeks 14 and 52 post-first sipuleucel-T infusion.
- k. PTT, PT/INR

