### 8.5.2 Secondary Endpoint(s)

#### 8.5.2.1 Secondary Immune Endpoint(s)

- The mean peripheral PA2024-and PAP-specific T-cell proliferation using a  $^3\text{H}$ -thymidine incorporation assay reported as SI at baseline and 6, 10, 14, 26, 39, and 52 weeks after the first infusion of sipuleucel-T.
- The mean peripheral PA2024-and PAP-specific T-cell activation to sipuleucel-T using interferon gamma ( $\text{IFN}\gamma$ ) enzyme-linked immunosorbent spot (ELISPOT) at baseline and weeks 6, 10, 14, 26, 39, and 52 weeks after the first infusion of sipuleucel-T.

Version 4.0 Date: 08/21/2020

NCT02463799

The values for radium-223 in this protocol has been revised as per the US NIST standardization update (agreed on 17 Mar 2015)

- The mean PA2024-and PAP-specific antibody (IgM and IgG) response to sipuleucel-T using enzyme-linked immunosorbent assay (ELISA) at baseline and weeks 6, 10, 14, 26, 39, and 52 weeks after the first infusion of sipuleucel-T.
- Product immune parameters including CD54 + cell counts and upregulation and total nucleated cell (TNC) counts.

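### The primary week-6 t test does not use the baseline PA2024 SI already scheduled in both arms: a cheap possible improvement, not an error

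*Combined protocol and SAP*

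**What the plan says.** - **Primary test (8.6.3).** "We will compute the logarithms of each patient's SI and use these data in a t test to compare the two groups". No covariate is named.
- **Power basis (8.2).** 15 per group, a 3.6-fold ratio, 80% power, one-sided 0.05, lognormal SI with SD 1.4 in each group.
- **Baseline is collected.** Section 3.0 says of immune monitoring that "samples will be drawn at screening and at 6, 10, 14, 26, 39, and 52 weeks after the first infusion of sipuleucel-T", in both arms. Section 8.5.2.1 (immune) lists PA2024 and PAP proliferation "reported as SI at baseline and 6, 10, 14, 26, 39, and 52 weeks after the first infusion of sipuleucel-T".
- **When baseline is drawn.** Footnotes to both schedules in 6.1 also allow the draw at a day-one visit before dosing. Each leukapheresis is "followed approximately 3 days later by an IV infusion of sipuleucel-T" (3.0), and the Arm 2 schedule puts the first pre-leukapheresis visit and the first infusion both at week 0.
- **The only baseline definition in section 8** is in 8.6.4.2. It covers laboratory data and takes the last non-missing value up to the randomization date.
- **Secondary model (8.6.3).** The repeated-measures model has arm, visit and their interaction. It names no baseline covariate and does not say whether baseline counts as a visit.

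**The concern.** With 15 per arm and a log-scale SD of 1.4, chance differences between arms in pre-treatment SI can be sizeable. If baseline SI predicts week-6 SI, an unadjusted comparison carries that imbalance into the estimated ratio and leaves explainable variance in the error term. The covariate needs no new sample or visit, so its omission without a stated reason deserves a check.

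Two loose ends come with it. A baseline SI for adjustment is not pinned down: an Arm 2 draw made on day one just before infusion could fall after the first leukapheresis. And if the repeated-measures model counted baseline as a visit, its arm main effect would average in a time point at which no treatment effect can exist.

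**Working it through.** **Inputs.** From 8.2: n = 15 per arm, ratio 3.6 so δ = ln 3.6 = 1.281, SD 1.4 (read as the SD of natural-log SI), one-sided α = 0.05. The correlation ρ between baseline and week-6 log SI is not in the documents. It is an assumption, shown over a range.

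**1. The plan's figure.** SE = 1.4 × √(2/15) = 0.511 and δ/SE = 2.506. The normal approximation gives 80.5%; the noncentral t with 28 df gives 78.8%. The stated 80% reproduces, and 78.8% is the comparator below.

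**2. ANCOVA.** The residual SD is 1.4 × √(1 − ρ²) on 27 df. Chance baseline imbalance multiplies the variance of the arm difference by 1 + T²/28, where T is the two-sample t statistic for baseline. Power is averaged over T ~ t(28).

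| ρ | ANCOVA power | Change from 78.8% (points) |
|---|---|---|
| 0 | 77.4% | −1.4 |
| 0.1 | 77.8% | −1.0 |
| 0.2 | 78.9% | +0.1 |
| 0.3 | 80.7% | +1.9 |
| 0.4 | 83.4% | +4.6 |
| 0.5 | 86.9% | +8.1 |

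Break-even is at ρ = 0.195. Simulation with 200,000 trials per value agrees at ρ = 0, 0.2 and 0.5.

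**3. The 1.4 points is an average over randomisations.** At ρ = 0 and T = 2 the variance factor is 1 + 4/28 = 1.143. The SE becomes 0.511 × √1.143 = 0.546 and power falls to 73.9%, a loss of 78.8 − 73.9 = 4.9 points.

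**4. What ρ might be.** Baseline precedes on-study exposure to a product "activated in vitro with prostate antigen PA2024", and the interval is long. From a day-one draw to the week-6 sample it is about 6 to 7 weeks in Arm 2. In Arm 1, "First sipuleucel-T infusion may occur any time between the second and third radium-223 infusion", that is weeks 4 to 8, so the interval is 4 + 6 = 10 to 8 + 6 = 14 weeks. A screening draw adds more: "All screening procedures must occur within 28 calendar days prior to registration". A low ρ, or one lower in Arm 1, is plausible. Simulated common-slope ANCOVA power with ρ in Arm 1 / Arm 2 is about 78% at 0/0.3, 79% at 0.1/0.3, 82% at 0.2/0.5 and 83% at 0.3/0.5. Type I error stays near 5%.

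**5. Chance imbalance in the unadjusted estimate.** The slope is ρ × 1.4/SD_baseline, and a 1-SE imbalance is SD_baseline × √(2/15). The baseline SD cancels, leaving a shift of ρ × 0.511 on the log scale. The SI ratio moves by exp(0.511ρ) = 1.05, 1.17 and 1.29 at ρ = 0.1, 0.3 and 0.5.

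**6. Missing baselines.** With two missing per arm, filled with the mean pooled over arms, simulated power is about 77%, 80% and 86% at ρ = 0, 0.3 and 0.5, with type I error near 5%.

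**7. Repeated-measures model.** If baseline were one of seven visits, a constant 3.6-fold ratio at the other six would appear in the arm main effect as 3.6^(6/7) = 3.00-fold.

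**The case against.** The strongest reply is that the plan contains no mistake. The primary test is prespecified, its scale is stated, and it matches the sample-size basis. The benefit of adjustment rests wholly on a correlation that the documents do not give and that may be low. Below about 0.2, ANCOVA is slightly worse. To set the loss at ρ = 0 against gains at 0.3 to 0.5 says nothing about which case is more likely. All of this stands, and it is why the point is an improvement and not a correction.

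A late change of primary test also has a credibility cost, because 10.5 has the principal investigator review efficacy endpoints. This stands too, and it sets the condition in the fix.

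Baseline SI is a listed secondary endpoint, so an imbalance would be visible. That is true, but visibility is not adjustment. The 8.6.4.2 definition could be borrowed, but it is written for laboratory data and stops at randomization, so it would miss a later day-one draw. The post-leukapheresis Arm 2 draw is only a possibility, and no effect of it on SI is shown.

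The 3.00-fold dilution is conditional as well. Under a constant ratio, complete data, SD 1.4 and compound symmetry, the plan's interaction rule would switch to by-visit contrasts in about 35%, 49% and 66% of trials at within-subject correlation 0, 0.3 and 0.5.

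**Conclusion.** The point holds as a cheap improvement. Under the 8.2 inputs, ANCOVA costs about 1.4 points of power on average if baseline is uninformative, breaks even near ρ = 0.2, and gains about 1.9 to 8.1 points for ρ from 0.3 to 0.5. It would also remove the influence of a chance imbalance, which at 1 SE moves the unadjusted ratio by a factor of 1.05 to 1.29 for ρ from 0.1 to 0.5.

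A reader might infer more than this, and the documents do not support it:

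- **That the t test is biased or the trial underpowered by the omission.** The test is valid under randomisation and the stated power reproduces.
- **That ANCOVA would raise power.** No value of ρ is given, and the unequal-arm cases at 0/0.3 and 0.1/0.3 show essentially no gain.
- **That 1.4 points caps the loss in any one trial.** It is an average, and a large chance imbalance costs more.

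The repeated-measures point is secondary, conditional, and a matter of clarifying the text.

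**What to change.** Add to 8.6.3, for example:

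> Week-6 log SI will be compared between arms by ANCOVA with terms for arm and log baseline PA2024 SI, one-sided at the 0.05 level. Baseline SI is the last sample drawn before the first leukapheresis or the first radium-223 infusion, whichever comes first. A subject without such a sample is retained, with log baseline SI set to the mean pooled over both arms.

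- **Role of the ANCOVA.** Make it primary, with the t test as sensitivity analysis, only if a written amendment documents that no comparison of SI by arm has been seen. If that cannot be stated, keep the t test as primary and add the ANCOVA as a labelled sensitivity analysis.
- **Baseline.** Align the Arm 2 schedule footnote on the baseline draw with this definition, and note that the 8.6.4.2 definition applies to laboratory data only.
- **Repeated-measures model.** State that it uses post-baseline visits only, with log baseline SI as a covariate.
- **Other assays.** 8.6.3 ties their analysis to the primary method, so say whether they follow the change.

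The cost is one amendment approved by the investigators and the IRB or IEC (10.6) across 4 to 5 centers, with no new samples or visits. If the ANCOVA becomes primary, it also costs one degree of freedom and, if baseline proves uninformative, the average 1.4 points of power. As a sensitivity analysis it costs the primary test no power.
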